7.2 Data Collection

The following table represents data that will be collected during the study.

Studies	First day of conditioning [@]	Day 0 (Graft Infusion)	Day 7	Day 14	Day 28 or Discharge [%]	Day 56	Day 120
Review of LBP or placebo administration #	X	X	X	X	X	X	----
Use of TPN/EN (yes or no and days of administration)	X	X	X	X	X	X	X
Use of antimicrobial agents	X	X	X	X	X	X	X
Bloodstream infection	X	X	X	X	X	X	X
Clostridium difficile -associated diarrhea	X	X	X	X	X	X	X

[@]The first day of the transplant conditioning regimen is defined as the first day of chemotherapy or TBI, excluding any preceding anti T-lymphocyte antibody therapy. See [Section 4.2.1](#).

[%] Day 28 or day of discharge, whichever comes first.

[#] Total days product was administered will be collected for each reporting period. See [Section 4.2.2](#).

7.3 Correlative Studies

7.3.1 Serum citrulline levels

Serum specimens will be evaluated for citrulline levels by the laboratory of [name] at CUMC. Serum citrulline will be evaluated from the initiation of therapy to Day 56. Given previous experience, it is predicted that serum citrulline levels are expected to nadir at Day 7 and not begin to rebound until Day 21 in patients receiving placebo. In comparison, it is predicted that patients receiving *LBP* will have a less profound decrease in mean serum citrulline at Day 7 and earlier kinetic rebound in mean serum levels, reflecting less mucosal insult as hypothesized. Given the proposed effect in maintaining and/or attenuating injury to intestinal luminal integrity, it is hypothesized that maintaining higher serum citrulline levels in patients receiving *LBP* will be associated with less GI aGvHD and less mucosal barrier insult blood stream infections (MBI BSI).

7.3.2 Intestinal flora phylogenetic composition

Evaluation of the intestinal flora will be from the initiation of *LBP* therapy to Day 120. DNA from each stool specimen collected will be extracted and purified as we have performed previously.³⁴ Phylogenetic profiling using 16S rRNA gene sequencing will be performed on the Illumina MiSeq platform with 175 bp paired end reads of V4-V5 region amplicons. Sequence data will be compiled and processed using mothur⁷⁴ and QIIME⁷⁵, screened and filtered for quality,⁷⁶ then classified to the species level⁷⁷ using the Greengenes reference database.⁷⁸

7.3.2.1 **Evaluating baseline colonization with *LBP*, loss of *LBP* during the course of hospitalization, re-colonization rate with *LBP* introduction and persistence of re-colonization**

Evidence of baseline colonization with *LBP* in our experience at MSKCC is uncommon. In 230 adult patients admitted for alloHCT, only 24 (10%) had detectable levels of *LBP* as measured by 16S deep sequencing. Pediatric patients will have a somewhat higher baseline colonization rate with *LBP*.⁷⁹ *LBP* strains isolated from the flora of healthy individuals have generally been reported to be antibiotic-sensitive with notable exceptions

of resistance to streptomycin, tetracycline, levofloxacin, and vancomycin being notable exceptions.⁸⁰ The vast majority of isolates are beta-lactam sensitive. Thus, we predict that during the course of alloHCT, patients who at baseline are colonized with *LBP* and require broad-spectrum antibiotic therapy for treatment of febrile neutropenia will demonstrate loss of commensal *LBP*. Because patients will continue to be administered *LBP* beyond transplant hospitalization (and after discontinuing antibiotic therapy often given during this hospitalization), we also predict that ***LBP* introduction will lead to improved recovery of *LBP* abundance** and that introduction will lead to persistent colonization.

7.3.2.2 **Evaluating the effects of *LBP* introduction on the abundance of other members of the intestinal flora**

LBP species are known to produce lactate via fermentation of a variety of sugars.⁴⁶ Lactate, in turn, can support other strains of bacteria, contributing to bacterial diversity. Bacterial strains with demonstrated lactate utilization can in turn produce butyrate,⁸¹ which can mediate anti-inflammatory effects through recruitment of regulatory T cells (Tregs).⁸²⁻⁸⁴ Species that can utilize lactate include relatives of *Eubacterium halli* and *Anaerostipes caccae*.⁸¹ *LBP* species have also been found in animal models to mediate suppression of potentially pathogenic commensal bacteria, such as *E. coli*, within the intestinal tract,⁸⁵ perhaps via promoting augmented IgM and IgA responses against these pathobionts. Bacteria including *E. coli* and its relatives from the phylum Proteobacteria have been observed to commonly expand and dominate the intestinal tract in patients following allo HCT⁸⁶ and have been found to be associated with aggravated GvHD in animal models²³ and increased mortality in allo HCT patients.³⁷ In a similar manner, introduction of *Lactobacillus* species have also been observed in animal models to suppress the expansion of *Enterococcus* species,³⁵ leading to reduced GvHD. Enterococcal expansion, similar to Proteobacterial expansion, has been implicated in mediating aggravated GvHD in allo HCT patients.⁸⁷ Based on these prior results reported in the literature, we predict that *LBP* introduction will promote bacterial diversity by supporting the abundance of lactate utilizers and preventing domination by Proteobacteria and Enterococci. We will quantify microbial diversity using the Shannon diversity index⁸⁸ following closed-reference operational taxonomic unit picking.⁷⁵ We will also perform abundance comparisons evaluating for taxons modulated by *LBP* introduction using linear discriminant analysis (LDA) effect size (LEfSe) analysis.⁸⁹ We will compare relative abundances, determined by 16S deep sequencing, as well as absolute abundances by utilizing relative abundance data combined with quantitative total 16S gene levels using validated primers.⁹⁰

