Incidence of non-*Lactobacillus* bacteremia (20%) and *Clostridium difficile*-associated diarrhea (CDAD, 20%) did not exceed published rates in pediatric alloHCT recipients.⁶³⁻⁶⁶ Microbial pathogens associated with bacteremia or fungemia included: *Staphylococcus epidermidis* (1), *Serratia marcescens* (1), *Enterococcus faecium* (1), *Klebsiella pneumoniae* (3), *Streptococcus viridans* (1), and *Fusarium species* (1). Up to four weekly stool samples were collected from 22 patients receiving *LBP*. Of these patients, the majority (96%, 21/22) had at least one stool specimen that was positive for *Lactobacillus*. In this restricted analysis, 75% stool specimens (77/102) were positive for *Lactobacillus*, suggesting *LBP* administration colonized patient stool. The pilot study also found *LBP* administration was feasible during alloHCT. *LBP* was administered successfully to 97% (30/31, 95% CI (83%-100%)) of enrolled children whom received at least 50% of the total intended dose of probiotic. Among the 30 evaluable patients, the mean and median percent of doses taken were $92 \pm 14\%$ and 97% (range 50-100%), respectively.

Nine patients (9/30, 30%) developed clinically significant (Grade II–IV) aGvHD. Five patients (5/9, 56%), experienced Grade II aGvHD, and 4 patients (4/9, 44%) experienced Grade III aGvHD. No patient experienced Grade IV aGvHD. Overall incidence of GI aGvHD was 23%, which is lower than some published literature.¹ Importantly, the pilot study provides reasonable evidence that *LBP* administration did not increase the incidence of aGvHD and legitimates further investigation into defining its effects on GI aGvHD.

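### Section 7.3.2.2 asks about the rest of the flora but states no removal of LBP reads, so Shannon diversity and relative-abundance comparisons can shift in the LBP arm during dosing with no other organism changing

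*Combined protocol and SAP*

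**What the plan says.** The second part of Section 7.3.2 is headed as an evaluation of LBP "introduction on the abundance of other members of the intestinal flora". Its prediction is that LBP "introduction will promote bacterial diversity by supporting the abundance of lactate utilizers and preventing domination by Proteobacteria and Enterococci".

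Three measures are named:

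- **Diversity:** "We will quantify microbial diversity using the Shannon diversity index", after closed-reference OTU picking.
- **Taxon screening:** "We will also perform abundance comparisons evaluating for taxons modulated by *LBP* introduction", by LEfSe. The input scale is not stated.
- **Abundance:** "We will compare relative abundances, determined by 16S deep sequencing, as well as absolute abundances by utilizing relative abundance data" combined with total 16S gene levels.

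The only filter described in Section 7.3.2 concerns sequence quality. Classification goes down to species. Neither Section 7.3.2 nor the plan for Exploratory Aims 3 and 4 in Section 9.3 says whether LBP reads stay in or come out. Section 9.3 gives no arm comparison of Shannon diversity; it describes correlations and Cox regression with genes, pathways and metabolites. Domination is not defined, and neither abundance scale is given precedence.

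Dosing runs from the first day of conditioning through Day 56 (Section 4.2.1). Stool is scheduled before conditioning and on Days 0, 7, 14, 28 (or discharge), 56 and 120 (Section 7.4.2). In the pilot, "75% stool specimens (77/102) were positive for" *Lactobacillus* (Section 2.5).

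**The concern.** The question is about organisms other than LBP, but LBP is itself one of the organisms counted. It is swallowed daily in one arm only, and five of the seven scheduled stools (Days 0 to 56) fall within the dosing period. If the OTU table is used unfiltered, the outcome in the LBP arm contains the intervention.

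Two distortions follow. Adding one taxon changes the Shannon index directly, and it shrinks every other taxon's share of reads. In a flora dominated by one pathogen, both changes look like the predicted benefit: more diversity, less domination. Section 2.3 puts restored diversity and preserved epithelial integrity at the centre of how probiotics might prevent aGvHD, so a partly built-in rise would be read as mechanistic support. In a diverse flora with much LBP the index falls instead, which could hide a real benefit.

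**Working it through.** **Inputs.** The plan gives no effect size, power or read share for Shannon or 16S abundance, so there is no planned figure to reproduce. LBP's share of reads (f) and the Shannon index of the remaining flora (H, natural logs) are assumptions, shown over a range. The pilot's 77/102 = 75.5% is positivity for the genus and says nothing about f. It also needs care as a count: up to four samples from 22 patients is at most 22 x 4 = 88, fewer than 102.

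**Step 1: Shannon.** Leave the other organisms unchanged and let LBP take a fraction f of reads. Then

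H' = (1 - f)H + h(f), where h(f) = -f ln f - (1 - f) ln(1 - f).

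Worked cases:

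- H = 0.5, f = 1%: 0.99 x 0.5 + 0.056 = 0.551, +10%.
- H = 0.5, f = 10%: 0.9 x 0.5 + 0.325 = 0.775, +55%.
- H = 3, f = 50%: 0.5 x 3 + 0.693 = 2.193, -27%.

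Change in Shannon with no change in any other organism:

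| f | H = 0.5 | H = 1 | H = 2 | H = 3 |
|---|---|---|---|---|
| 0.1% | +1.5% | +0.7% | +0.3% | +0.2% |
| 1% | +10% | +5% | +2% | +1% |
| 5% | +35% | +15% | +5% | +2% |
| 10% | +55% | +22% | +6% | +1% |
| 20% | +80% | +30% | +5% | -3% |
| 50% | +89% | +19% | -15% | -27% |

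H' peaks at ln(1 + e^H), when f = 1/(1 + e^H). For H = 2 the peak is 2.127 at f = 12%, so the rise never exceeds about 6%.

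**Step 2: relative abundance.** A taxon with share p falls to (1 - f)p. At f = 10%, a taxon at 90% reads as 0.9 x 0.90 = 81%, and one at 33% reads as about 30%.

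**Step 3: absolute abundance.** If the other flora carries total 16S level T, adding LBP makes the total T/(1 - f). The estimate for a taxon is (1 - f)p x T/(1 - f) = pT. It does not change, so comparisons of single taxa on this scale are free of the dilution.

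**Step 4: effect of removing LBP reads.** Take one taxon at 90% and ten at 1%, so H = 0.555. With LBP at 10% of reads, H' = 0.9 x 0.555 + 0.325 = 0.825 and the dominant share is 0.81. Dropping LBP and dividing the rest by 0.9 restores 0.81/0.9 = 0.90 and H = 0.555. The spurious change is exactly zero.

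**The case against.** **Inclusion of LBP reads is inferred from silence.** This stands. A reader might infer that the plan chooses to compute on all reads; it does not say so. What can be said is that no removal is stated, and an unfiltered table is what results if the text is followed as written.

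**The domination question is already protected.** This stands for absolute abundances, which Section 7.3.2.2 plans next to the relative ones. The stronger reading, that a fall in pathogen domination would be spurious, is not supported on that scale. It remains true that no scale takes precedence and domination is undefined.

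**The artefact can be recognised and undone.** This largely stands. One might conclude that an arm difference in diversity could not be told apart from the product in the stool. But Section 7.3.2.1 follows LBP abundance with the same 16S profiling, and with f known, H = (H' - h(f))/(1 - f). The Day 120 stool is also scheduled 64 days after dosing ends, although Section 7.3.2.1 predicts persistent colonisation, so it may not be free of LBP. Neither safeguard appears as a planned step in the diversity analysis.

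**The size may be trivial, and the direction is not fixed.** Both stand. At f = 0.1% the change is 1.5% or less at each H in the table, and at high H it can be negative.

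**Whole-community diversity is legitimate.** It is, for Aim 1.2.3, which concerns the composition of the flora as a whole. It does not answer the narrower question "on the abundance of other members of the intestinal flora", so both versions are needed.

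**Conclusion.** The concern holds in limited form. For the question Section 7.3.2.2 asks, Shannon and relative-abundance LEfSe on an unfiltered table can differ between arms during dosing solely because LBP is in the stool. The change ranges from negligible (f near 0.1%) to large and positive in a low-diversity flora (+35% at f = 5% and +55% at 10%, with H = 0.5). It is at most about +6% at H = 2, and negative at H = 3 once f is high. These sizes rest on assumed f and H and on the rest of the flora being unchanged.

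It would be wrong to conclude that the bias always favours LBP, or that the pilot's positivity rate shows it to be large; the documents support neither. The absolute-abundance comparisons are sound on this point. The aim is exploratory, and the primary endpoint, sample size and alpha are untouched. The change is still worth making because it fits the analysis to its own stated question at almost no cost.

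**What to change.** In Section 7.3.2.2 and the Exploratory Aim 3 analysis in Section 9.3, state before arm-level data are seen that:

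1. For the question about the rest of the flora, reads assigned to *L. plantarum* are removed from every sample in both arms, the remainder is renormalised, and Shannon and relative-abundance LEfSe are computed on it.
2. The all-reads version is reported alongside as the whole-community measure for Aim 1.2.3.
3. Statements about Proteobacteria and Enterococcus domination rest on the LBP-excluded or the absolute scale.

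LBP abundance needs no new output, since Section 7.3.2.1 already covers it.

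The cost is one filtering step on taxa already to be classified to species, and a few sentences of text. No further samples or sequencing are needed. The small downside is that naturally carried *L. plantarum* is also removed (24/230, about 10%, of adults at baseline in Section 7.3.2.1; somewhat more is expected in children). The same rule applies in both arms.

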7.3.3 Evaluating functionality of the intestinal flora

While isolates with near-identical 16S rRNA gene sequences tend to share many traits, they can often have variable gene content and as a result variable properties, even strains that are considered to be the same species.⁹¹ Thus phylogenetic data can at best only provide an approximation of gene content and function. To further our understanding of how *LBP* can potentially reduce the risk of aGvHD in pediatric HCT recipients, we propose two targeted discovery approaches designed

to explore and identify mechanisms by which *LBP* may mediate a beneficial effect. These approaches include whole shotgun metagenomic sequencing and commercially available functional metabolite profiling.

7.3.3.1 **Evaluating the effects of LBP introduction on intestinal flora function via whole shotgun metagenomics sequencing to identify bacterial genes and gene pathways associated with modulation of GvHD**

Identifying mechanisms by which bacteria can modulate human phenotypes remains a formidable challenge in the microbiota field. One promising approach is metagenomic sequencing of whole community DNA,⁹¹ or “shotgun sequencing.” Whole shotgun metagenomic sequencing provides bacterial gene abundance data, which allows quantification of the abundance of individual genes and gene pathways. Following identification of bacterial DNA sequences, sequences are mapped against a reference database, such as the Kyoto Encyclopedia of Genes and Genomes (KEGG) database,⁹² to identify bacterial enzymes in metabolic reference pathways. This approach has recently identified pathways that are enriched in the flora of patients with Type 2 diabetes mellitus,⁹³ obesity,⁹⁴ and newly-diagnosed Crohn’s Disease.⁹⁵

We will randomly select a subset of 30 samples from patients with similar overall 16S abundance, but 15 samples will have abundant *LBP* and 15 additional samples will have undetectable *LBP*. We will utilize the Illumina HiSeq2000 platform, aiming for a mean of 10 gigabases of 101 bp paired-end reads per sample. For comparative quantification of gene content at the individual gene level and the level of KEGG metabolic pathways, we will utilize linear discriminate analysis (LDA) effect size (LEfSe) analysis⁸⁹ for biomarker discovery. In addition to comparing samples with abundant and reduced *LBP* levels, we will also examine samples from patients who did or did not develop aGvHD. With this approach, we hope to identify novel bacterial genes and gene pathways, some of which may be *LBP*-derived, that are associated with modulation of aGvHD and may play a role in aggravating or attenuating inflammation. As all correlative assays will be performed on the backbone of a COG clinical trial, we anticipate high quality and very complete assessment laboratory findings.

7.3.3.2 **Evaluating the effects of LBP introduction on intestinal flora function via functional metabolite profiling**

While whole shotgun metagenomic sequencing provides information regarding the functional potential of the intestinal flora, a complementary approach is to assay directly for demonstration of substrate utilization and metabolite production. By determining bacterial metabolite abundances, one can confirm that increased abundance of individual genes and genes of metabolic pathways are associated with a corresponding increase in enzymatic activity. This method can also identify novel bacterial metabolites that are biologically active. One example of a group of metabolites that have garnered interest recently is short-chain fatty acids (SCFA), which are produced by many bacteria as a byproduct of carbohydrate fermentation. SCFA have been found to be important modulators of the immune system. In germ-free mice and vancomycin-

treated conventional mice, administration of SCFA (acetate, propionate, or butyrate) restored normal numbers of Tregs in the large intestine.⁸⁴ GPR43 (a SCFA receptor) has been identified as necessary for mediating the anti-inflammatory effects of commensal bacteria⁹⁶ and is required for restoration of large intestinal Tregs by SCFA.⁸⁴ We will quantitatively profile levels of enzymatic substrates and metabolites via UHPLC-MS services coupled with an extensive library with >2800 authenticated compounds provided by Metabolon (Durham, NC). We will profile aliquots of the same stool samples selected for the whole shotgun metagenomic sequencing approach detailed above as well as paired serum samples collected at the same time as the stool samples. A recent study linking intestinal flora with severity of an autism-like syndrome in mouse models similarly utilized Metabolon's services to identify a serum metabolite that induced anxiety-like behavior in these mice. Interestingly, the levels of this metabolite were modulated by intestinal flora composition.⁹⁷ Using this approach, we will **identify novel bacterial metabolites, some of which may be LBP-derived, that are associated with modulation of aGvHD** and may play a role in either aggravating or attenuating inflammation.

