2.3 An emerging role for the intestinal microbiota in GI aGvHD: Probiotic therapy

Commensal organisms within the GI tract, collectively known as the intestinal microbiota, are predominantly comprised of two phyla, *Bacteroidetes* and *Firmicutes*, the latter of which includes the microbial order *Lactobacillales*.³¹ The intestinal microbiota critically

functions in maintaining the physical, functional, and immunologic barriers within the GI tract such that perturbations in microbiota diversity or dysbiosis result in aberrant systemic immune response³² as well as pathogen colonization and mucosal invasion.³¹ For example, dysbiosis induced by broad-spectrum antimicrobial therapy causes life-threatening infections from *Clostridium difficile*³³ and vancomycin-resistant *Enterococcus*³⁴ in alloHCT recipients. In addition, aGvHD markedly alters the intestinal microbiota in mice and in human alloHCT recipients, decreasing intestinal microbial diversity and increasing predominance of enteric pathogens.³⁵ As a result, aGvHD increases the risk of bacteremia with enteric pathogens resulting from mucosal barrier injury (MBI).^{36,37} Furthermore, loss of microbial diversity is an independent risk factor for mortality following alloHCT. Specifically, lower microbial diversity at the time of engraftment significantly associates with decrease in overall survival (OS) and increase in transplant-related mortality (TRM), particularly from aGvHD and infection.³⁷

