7.1 Required Clinical and Laboratory Evaluations

Studies	Eligibility [§]	First day of conditioning ^{@.&}	Day 0 (Graft Infusion)	Day 7	Day 14	Day 28 or Discharge [%]	Day 56	Day 120
History	X	----	----	----	----	----	----	----
Physical examination, evaluation of GvHD	X	X	X	X	X	X	X	X
Performance status	X	----	----	----	----	----	----	----
Pregnancy test*	X	----	----	----	----	----	----	----
Screening for Clostridium difficile (only if diarrhea at enrollment or first day of conditioning)	X	X ^{&}	----	----	----	----	----	----
Review of LBP administration/patient diary	----	----	X	X	X	X	X	
Blood sample for citrulline and cytokine studies See Section 7.4.1	----	X [^]	X	X	X	X	X ^{a,b}	
Stool sample for correlative studies See Section 7.4.2	----	X [^]	X	X	X	X	X ^b	X ^b

§ All clinical and laboratory studies to determine eligibility must be performed within 7 days prior to enrollment/randomization unless otherwise indicated.

^ Specimen collection on first day of conditioning or anytime within 72 hours before the start of conditioning (prior to chemotherapy). See [Section 7.4.1](#) and [Section 7.4.2](#) for overview of procedures and a Specimen Collection Manual available on the COG protocol web page with further technical detail.

@ The first day of the transplant conditioning regimen is defined as the first day of chemotherapy or TBI, excluding any preceding anti T-lymphocyte antibody therapy. See [Section 4.2.1](#).

% Day 28 or day of discharge, whichever comes first.

* Women of childbearing potential, defined as a female who has had her first menstrual cycle.

& If the patient has diarrhea on the first day of conditioning and repeat stool culture shows *C. diff*, then the patient is ineligible and must be removed from protocol therapy. Reminder: patient condition(s) prior to initiation of protocol therapy must be within parameters required for eligibility. (See [Section 8.1](#))

a Citrulline sample only.

b Blood and stool specimens may be collected within 14 days of the designated time point without being considered a protocol deviation.

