Exploratory Aims 3 and 4: These aims will examine the effects of *LBP* introduction on the intestinal flora of pediatric alloHCT recipients. The association between *LBP* administration and bacterial genes and pathways, and bacterial metabolites will be evaluated with Pearson's correlation coefficient with possible transformation to approximate normality. In addition to confirming the significance, a 95% confidence interval will be estimated for each marker. The total length of the interval depends on the observed correlation; the length will be 0.53 if the correlation is 0.40 and 0.24 if the correlation is 0.8. In addition to correlation, bivariate scatterplots will be used to display the association between *LBP* administration and each marker. Finally, we will perform a descriptive analysis examining the association between GvHD outcomes and bacterial genes, pathways, and metabolites using Cox regression. Additional regression models will adjust for other known GvHD risk factors.

Exploratory Aim 5: This aim will examine the effects of *LBP* on pro-inflammatory cytokines in alloHCT recipients. We hypothesize that *LBP*-associated maintenance or restoration in the microbiota will attenuate serum levels of pro-inflammatory cytokines in the early post-transplant period. We will use the same analytic approach as described for exploratory Aim 2 above.

Exploratory Aim 6: This aim will examine the effects of LBP on the incidence (yes/no) of *Clostridium difficile*-associated diarrhea in alternative donor HCT patients. Patients who have at least one incidence (positive) of *C. diff* during any reporting period is considered evaluable for this aim. We will compare proportion of *C. diff* during the study period between arms via the chi-square test.

Exploratory Aim 7: This aim will examine whether LBP administration reduces hospital days within the first 120 days post hematopoietic cell transplant. Total hospital days over the study period is calculated as the duration between the date of admission for conditional therapy and the date of discharge (or the study end date). Hospital days will be compared between arms by t-test (or Wilcoxon rank-sum test if assumptions for t-test are not met).

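### The 30-sample metagenomic and metabolite draw is not balanced on visit and does not require samples to precede aGvHD onset, so the exploratory LBP contrast is mixed with transplant phase

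*Combined protocol and SAP*

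**What the plan says.** Section 7.3.3.1 gives the whole selection rule: "We will randomly select a subset of 30 samples from patients with similar overall 16S abundance", split into 15 samples with abundant LBP and 15 with undetectable LBP. The groups are defined by LBP measured in the sample, not by randomized arm. The rule does not mention visit, number of samples per patient, or timing relative to aGvHD.

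The available pool is wide. Section 7.3.2 states: "Evaluation of the intestinal flora will be from the initiation of *LBP* therapy to Day 120". Section 7.4.2 lists seven stool time points: start of conditioning (up to 72 hours before it), Days 0, 7, 14, 28 (or discharge), 56 and 120. Dosing runs from the first day of conditioning through Day 56 (section 4.2.1).

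Three further uses follow:

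- In section 7.3.3.1, besides the LBP contrast, "we will also examine samples from patients who did or did not develop aGvHD".
- In section 7.3.3.2, metabolites are profiled in the same selected stools, "as well as paired serum samples collected at the same time as the stool samples".
- In section 9.3, Exploratory Aims 3 and 4 include a descriptive analysis "examining the association between GvHD outcomes and bacterial genes, pathways, and metabolites using Cox regression", with further models adjusting for known GvHD risk factors.

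On blood, sections 7.1 and 7.4.1 schedule no draw at Day 120, and section 7.1 labels Day 56 "Citrulline sample only".

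**The concern.** There are two separate problems.

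**Phase.** Stools taken before the first dose will mostly show no LBP, because baseline carriage is uncommon, so they fall into the undetectable group. Stools with LBP come mainly from treated patients while on product, after conditioning has begun and often under antibiotics. A gene or metabolite that changes with conditioning, antibiotics or time since transplant would then differ between the groups with no LBP effect. Because the groups are not the randomized arms, randomization gives no protection. Matching on overall 16S abundance equalises bacterial load, which is not the same as phase.

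**Direction.** Section 2.3 states that "aGvHD markedly alters the intestinal microbiota in mice and in human alloHCT recipients". The outcome window, Day 0 to Day 120 (section 9.2), overlaps the stool visits. Without a condition that the sample precede onset, a change caused by aGvHD could be reported as something that modulates it.

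**Working it through.** **Figures in the plan.** The plan gives none for the visit mix. Its only numbers for this sub-study are the 95% interval lengths in section 9.3: 0.53 at r = 0.40 and 0.24 at r = 0.8. With the Fisher interval, tanh(atanh(r) ± 1.96/√(n−3)), n = 30 gives 0.618 and 0.283, while n = 40 gives 0.532 and 0.239. The stated lengths therefore fit 40 observations. Nothing below depends on this, but it is one reason not to assume that section 9.3 refers to the 30 samples.

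**Inputs for the visit mix**

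- Off-product detection 10%: 24 of 230 adults at baseline (section 7.3.2.1, which expects children to be somewhat higher).
- On-product detection 75%: 77 of 102 pilot stools (section 2.5). This is genus-level *Lactobacillus*.
- Assumed: 1:1 arms, equal numbers of stools per visit, detection as a proxy for abundance, and 10% detection in the placebo arm throughout.

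**Expected stools, counting one per arm at each visit**

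- Start of conditioning: LBP detected 2 × 0.10 = 0.2; undetected 2 × 0.90 = 1.8.
- Each on-product visit: detected 0.10 + 0.75 = 0.85; undetected 0.90 + 0.25 = 1.15.
- Day 120, if LBP-arm detection falls back to 10%: 0.2 and 1.8. If it stays at 75%: 0.85 and 1.15.

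**Share of each group that is off product**

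| Visits drawn from | Detected | Undetected |
|---|---|---|
| Start to Day 28 (4 on-product visits) | 0.2/3.6 = 5.6% | 1.8/6.4 = 28.1% |
| Start to Day 56 (5 on-product visits) | 0.2/4.45 = 4.5% | 1.8/7.55 = 23.8% |
| All seven, Day 120 at 10% | 0.4/4.65 = 8.6% | 3.6/9.35 = 38.5% |
| All seven, Day 120 at 75% | 1.05/5.30 = 19.8% | 2.95/8.70 = 33.9% |

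Out of 15, the second row is about 0.7 against 3.6 samples. Varying one input at a time (baseline detection 5–20%, on-product detection 60–90%) gives 2–8% against 22–27% through Day 56, and 3–10% against 26–31% through Day 28.

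**What this does to a test.** A simulation (4,000 runs, 15 against 15, rank-sum test at 0.05) used a marker with no LBP effect that takes one level at start of conditioning and Day 120 and another at Days 0–56. For shifts of 1, 2 and 3 SD, the proportion of false positives was:

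- all seven visits, Day 120 detection 10%: 10%, 21%, 27%;
- all seven visits, Day 120 detection 75%: 6%, 8%, 9%;
- start to Day 28: 8%, 12.5%, 16%;
- Days 0–56 only: 4–5% throughout.

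The last line follows by construction, since this marker does not vary within Days 0–56. Matching on visit would also cover a marker or a detection rate that does vary there.

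**Samples after onset.** At the planned GI aGvHD rates of 18% and 30% (section 9.4), 30 × 0.18 = 5.4 to 30 × 0.30 = 9 samples would come from patients with GI aGvHD. The documents give no onset distribution. For assumed onset on Day 20, 30, 40 or 60, the scheduled stools after onset are 3, 2, 2 or 1 of 7 if all visits count, but 1, 0, 0 or 0 of 5 if only visits through Day 28 count.

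**The case against.** The strongest reply is that section 7.3.3.2 already narrows the draw. The stools selected for sequencing are also those profiled with serum taken at the same time, and no blood is drawn at Day 120, so a natural reading excludes Day 120. That stands in part. The all-visit rows above, and the 2 or 3 of 7 post-onset stools, are upper figures. It is not written as a selection rule, however, and it leaves the start-of-conditioning stools in, so the 24% against 4.5% imbalance remains.

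A reader might infer that the plan uses post-onset samples to explain aGvHD. The documents do not say that; they fail to exclude such samples. A reader might also take the Cox analysis in section 9.3 to be run on these 30 samples, but that section does not name them.

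A third inference would be that every Day 56 and Day 120 stool lacks a serum pair. The Day 56 label may mean only that no cytokine assay is planned. Section 7.4.1 describes one collection procedure (6 mL, three aliquots) for all visits and assigns metabolite serum to none. The label needs reconciling, but it does not show that serum is absent.

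The inputs are soft. The 10% is from adults and the 75% is genus-level. The pilot denominator is also unclear: 22 patients with up to four weekly stools give at most 88, not 102. Matching on 16S abundance may reduce the phase imbalance by an unknown amount. Section 7.3.2.1 predicts persistent colonization, which favours the milder Day 120 row. The work is described as discovery, and section 9.3 separately relates LBP administration to the markers.

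**Conclusion.** The concern holds as a gap in the selection rule. Followed as written, the draw places pre-product stools mainly in the undetectable group: about 24% against 4.5% through Day 56, or 28% against 6% through Day 28. If Day 120 stools are drawn and detection falls back to 10%, the off-product shares are about 39% and 9%. The direction follows from low baseline carriage; the size rests on the assumed detection rates and equal sampling of visits. The aGvHD comparison, and the Cox analysis if it uses these samples, can include stools taken after onset.

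It would go too far to conclude that Aim 1.2.4 cannot be answered. This contrast, as specified, cannot separate LBP from transplant phase, or cause from consequence, but the LBP-administration analysis in section 9.3 is a different comparison. The primary endpoint, type I error, power, safety monitoring and the stage decision are untouched. The change is worth making because it is cheap and 30 samples leave little room to adjust afterwards.

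**What to change.** In section 7.3.3.1, state that:

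- each patient contributes at most one sample;
- abundant and undetectable samples are matched by visit, within on-product visits that have paired blood (for example Day 0 to Day 28; a single visit is one option), keeping the 16S criterion;
- any comparison on aGvHD uses only samples taken before aGvHD onset.

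In section 9.3, name the sample set used for Aims 3 and 4, and start Cox follow-up at the sample date among patients free of aGvHD at that date.

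Reconcile the paired-serum requirement in section 7.3.3.2 with the absence of Day 120 blood and with the Day 56 label in sections 7.1 and 7.4.1.

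This needs no new samples or assays and should be settled before samples are drawn. The cost is a smaller pool. Even at the screening-stage size of 60 per arm, under the detection rates above and with complete collection, a single on-product visit would give about 60 × 0.75 = 45 LBP-arm stools with LBP and 60 × 0.90 = 54 placebo stools without. Missing stools, the 16S criterion, the pre-onset condition and a stricter cut-off for abundance would reduce both. Visit matching does not turn this into a randomized comparison: groups set by measured LBP can still differ in antibiotic exposure, and the report should say so.
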